Multidimensional Family Therapy to reduce alcohol and drug use in adolescents, an individually randomised controlled trial with embedded internal pilot.

University of Kent; Teesside University

Principal investigator: [name]

Multidimensional Family Therapy to reduce alcohol and drug use in adolescents, an individually randomised controlled trial with embedded internal pilot.

Evaluation protocol

Evaluating institution: University of Kent/ Teesside

University

Principal investigator: [name]

Project title ¹	Multidimensional Family Therapy to reduce alcohol and drug use in adolescents, an individually randomised controlled trial with embedded internal pilot.			
Developer (Institution)	MDFT International / Ending Youth Violence Lab / Barnardo's			
Evaluator (Institution)	University of Kent / Teesside University			
Principal investigator(s)	[name]			
Protocol author(s)	[name], [name], [name], [name]			
Trial design	Two-armed individually randomised controlled trial with embedded internal pilot and implementation and process evaluation			
Trial type	Internal pilot / efficacy			
Evaluation setting	Community			
Target group	13-17 years old, who use alcohol and / or drugs and who have offended or are at risk of offending, resident in Newport and Bristol LA			
Number of participants	400, 200 in the MDFT group and 200 in the BAU group.			
Primary outcome and data source	Percent days abstinent from alcohol and/or substance use at month 6, derived from the time line follow back 28 days.			
Secondary outcome and data source	Percent days abstinent from alcohol and/or substance use at month 12, derived from the time line follow back 28 days. Self-reported violent offending behaviour (Self-Report Delinquency Scale) at months 6 and 12),			

Self-report Strengths and Difficulties Questionnaire (SDQ total score, prosocial score, emotional regulation, peer relationships, hyperactivity, conduct, externalising and internalising scores) at months 6 and 12.

Self-report Short Warwick Edinburgh Mental Wellbeing Scale (SWEMWBS) at months 6 and 12.

Alcohol and substance use problems at months 6 & 12, using the problem scale from the European School survey on Alcohol and Drugs (ESPAD).

Self-report Client Service Receipt Inventory (CSRI) to assess police involvement at months 6 and 12 (arrests, cautions, charges, court attendance), educational outcomes (suspensions, exclusions, managed moves) and employment status.

Protocol version history

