As part of the recruitment process Barnardo's will work with a variety of referral agencies to ensure equity of opportunity to engage in the research. Referral and recruitment data will be carefully monitored in terms of ethnicity, sex and disability status, including an assessment of those eligible but refusing consent, this will provide an early indication of any issues that may arise due to the recruitment practices.

Table 1: Trial design

Trial design, i	ncluding number of arms	Multidimensional Family Therapy to reduce alcohol and drug use in adolescents, an individually, two-arm randomised controlled trial with embedded internal pilot.		
Unit of r	andomisation	Individual young person		
Stratification variables (if applicable)		Geographic area (Bristol, Newport) Severity of substance use (Low/ medium risk, high risk) assessed using the GAIN-SS		
Duimour	variable	Percent days abstinent from alcohol and drugs		
Primary outcome	measure (instrument, scale, source)	Time line follow-back in the 28 days prior to the 6 month follow up.		
Secondary outcome(s)	variable(s)	Percent days abstinent from alcohol and drugs in the 28-days prior to the 12-month follow up Self-reported volume of violent offending behaviour at months 6 & 12. Behaviour: internalising behaviour (emotional regulation plus peer relationships subscales), externalising behaviour (hyperactivity plus conduct problems subscales) at months 6 & 12. Mental health and wellbeing at months 6 & 12. Alcohol and substance use problems at months 6 & 12.		

		Self-report Client Service Receipt Inventory (CSRI) to assess police involvement at months 6 & 12 (arrests, cautions, charges, court attendance), educational outcomes (suspensions, exclusions, managed moves) and employment status.		
	measure(s) (instrument, scale, source)	Offending: Self-report delinquency scale covering the previous 6-month (SRDS), violent offences are classed as carrying a weapon, robbery, assault, racial assault and fire setting. Behaviour: Strengths and difficulties questionnaire (SDQ), externalising behaviour and internalising behaviour. Mental health and wellbeing, Warwick-Edinburgh Wellbeing Scale-short form (WEMWBS-SF). Alcohol and substance use problems, European School Project on Alcohol and Drugs Problem Scale (ESPAD-PS). Self-report Client Service Receipt Inventory (CSRI).		
Baseline for	variable	Percent days abstinent from alcohol and drugs.		

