The YEF outcomes database for substance use contains five outcome measures: Alcohol Use Disorders Identification Test (AUDIT), Substance and Choices Scale (SACS), CRAFFT Substance Abuse Screening Test (CRAFFT), GAIN-I Substance Problems Scale, Adolescent Alcohol Involvement Scale (AAIS). AUDIT and AAIS are specific to alcohol only. All the measures in the YEF database are screening tools, the outcome is dichotomous, none measure frequency of use beyond simple ordinal values with broad categories and none have adequate psychometric evidence of sensitivity to change over time. The only suitable measure in the database that measures frequency of alcohol and/ or substance use is the substance use domain of the Global Assessment of Individual Need (GAIN). This instrument is delivered as a structured interview. It collects data over a 90-day retrospective period on the frequency of use of different substances. It is long, 100+ items, and repetitive. Only frequency of use of individual substances can be derived using GAIN, rather than overall substance use because a young person may use multiple substances in a day. This makes it difficult to operationalise as a primary outcome measure.

We propose assessing alcohol and/ or substance use with the Time Line Follow Back method (TLFB; (Sobell and Sobell, 1995)). The TLFB is conducted as a structured interview using a calendar to aid recall. TLFB has established validity and reliability for multiple substances (Martin-Willett R et al., 2020) over time periods ranging from one to 365 days. It has been specifically validated for use with adolescents (Levy et al., 2004) and college students

(Fishburne and Brown, 2006, Sobell et al., 1986). The TLFB has been used to collect data on cannabis use (Donohue et al., 2004), cigarette smoking (Gariti et al., 1998) risky sexual behaviour (Carey et al., 2001) and use of illicit substances (Hersh et al., 1999). The research team have experience of using the TLFB in adolescent populations (Coulton et al., 2023, Coulton et al., 2024), and it has been widely used in evaluations of MDFT (Dakof et al., 2015). The research team have used the TLFB in several RCT's to assess alcohol and substance use among school pupils (SIPS Jnr High, RISKIT), adolescents attending emergency departments (SIPS Jnr), adolescents involved in the criminal justice system (RISKIT-CJS) and adolescents in police custody (Reframe).

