In adolescent populations a standard TLFB with a recall period of 28 days. Frequency of use is calculated as percent days abstinent from alcohol and/ or other substances in the previous 28-days. It provides a fractional outcome and is far more detailed than standard measures of alcohol and substance use and can yield information on the overall frequency of alcohol and substance use, frequency of individual substances, quantity of use and periods of heavy episodic use. With a trained researcher the TLFB28 takes on average 10 minutes to complete.

The covariate for the primary outcome is assessed at eligibility and baseline using a Single Substance Use Question (SSUQ; (Levy et al., 2021)) over the past 28-days. This single frequency question reduces the burden on participants at baseline and addresses the issue of potential assessment reactivity, where the assessment of substance use in detail acts as a brief intervention. The SSUQ meets the criterion as a covariate for adolescent populations in that it is highly correlated with frequency of substance use derived from the primary outcome time line follow-back 28 (rho = 0.903 for alcohol and 0.830 for drugs).

Secondary outcomes

Self-reported violent offending will be assessed using the volume score of the Self-Report Delinquency Scale (SRDS; (Smith and McVie, 2003)) over the previous six months. This 19-item questionnaire has established psychometric properties (Fonagy et al., 2018) in this population and has a strong correlation (R=0.95) with police charges (McAra and McVie, 2007). Violent offences are classified as carrying a weapon, robbery, assault, racial assault and fire setting.

Emotional symptoms and behavioural difficulties will be assessed using the self-completed Strength and Difficulties questionnaire (SDQ; (Goodman, 1997)). This assesses behaviour across several domains including, conduct, hyperactivity, emotional regulation, peer relationships and prosocial behaviour and allows for the generation of two multi-component outcomes: internalising and externalising behaviours with the latter highly associated with current or future offending behaviour. We will assess total score, externalising behaviour, internalising behaviour. The outcome is widely used and has demonstrated excellent validity and moderate reliability in adolescent populations (Goodman, 2001). The SDQ is suitable for

completion by those aged 10-17 years and those with mild learning disabilities (Law and Wolpert, 2014).

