We will explore the relationship between alcohol and substance use and violent offending (**PRQ5**) by comparison of data derived from the TLFB for specific substances and the SRDS. This will enable decisions to be taken about whether specific substances should be the target of the efficacy trial. Data redundancy (**PRQ6**) will be explored by examining the pattern of missing data for each outcome.

We will explore business as usual (PRQ7) through interviews with key stakeholders across both sites, those that deliver business as usual and those that refer to their services. We will explore key questions around acceptability of the intervention, factors that facilitate or hinder participation, intervention delivery and outcome assessment (PRQ8, PRQ9) by conducting interviews with young people and parents/ carers, purposively sampling those who did not consent and those who consented but dropped out of the intervention or follow up. To explore how the intervention is sensitive to the sociocultural needs of the target population and determine potential culturally influenced barriers towards the acceptability of the intervention in relation to ethnicity and equity, as well as the presence of structural barriers, we will conduct in-depth qualitative interviews with young people from minority ethnic communities and other marginalised groups including those with SEND and LAC, as well as with staff, and providers. Thematic analysis (Braun and Clarke, 2006) will be used to elicit young people's experiences of the programme, in addition to staff, and service providers' perspectives, and how these experiences impact on the acceptability of the intervention. The findings will inform future adaptations of the intervention to various socio-cultural contexts.

Efficacy study analysis

The primary analysis will take the form of a fractional regression model, adjusted for baseline stratification variables and the baseline covariate.

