e) Performed poorly at school or work		⊢		⊢		 	
f) Victimized by robbery or theft		⊢	∐		.	 	 
g) Trouble with police	⊢	⊢	⊢		 	⊢	-
h) Hospitalised or admitted to an emergency room	⊢		⊢		 	·	-
i) Engaged in sexual intercourse without a condom	⊢	⊢	⊢	⊢	H	H	-님
j) Engaged in sexual intercourse you regretted the next day							🔲
	1	2	3	4	5	6	7

Motivation – Readiness Ruler

Single item readiness ruler

On the scale below enter how you feel right now about your substance use

1 2 3 4 5 6 7 8 9 10

I never think about my substance use Sometimes I think about using substances less often

I have decided to use substances less often I am already trying to use fewer substances My substance use has changed I use less than before

Family Relationships - Brief Family Relationship Scale

Responses True or False

Cohesion

- 1. In our family we really help and support each other.
- 2. In our family we spend a lot of time doing things together at home.
- 3. In our family we work hard at what we do in our home.
- 4. In our family there is a feeling of togetherness.
- 5. My family members really support each other.
- 6. I am proud to be a part of our family.
- 7. In our family we really get along well with each other.

Expressiveness

- 8. In our family we can talk openly in our home.
- 9. In our family we sometimes tell each other about our personal problems.
- 10. In our family we begin discussions easily.

Conflict

- 11. In our family we argue a lot. (R)
- 12. In our family we are really mad at each other a lot. (R)
- 13. In our family we lose our tempers a lot. (R)
- 14. In our family we often put down each other. (R)
- 15. My family members sometimes are violent. (R)
- 16. In our family we raise our voice when we are mad. (R)

Time Line Follow-Back - TLFB28 - completed using interview rather than self-complete

To help us evaluate your drug use, we need to get an idea of what your use was like in the past _____ days. To do this, we would like you to fill out the attached calendar.

- ✓ Filling out the calendar is not hard!
- √ Try to be as accurate as possible.
- ✓ We recognize you won't have perfect recall. That's OKAY.

✓ WHAT TO FILL IN

- The idea is that for each day on the calendar we want you to indicate whether you "used" or "did not use" drugs.
- On days when you did not use drugs, you should write a "0" in the box.
- On days when you did use drugs, you should put a "√" in the box.

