It's important that something is written for every day, even if it is a "0".

√ YOUR BEST ESTIMATE

- . We realize it isn't easy to recall things with 100% accuracy.
- If you are not sure whether you used a certain drug on a Thursday or a Friday of a certain week, give it
 your best guess! The goal is to get a picture of how many days you were using drugs and your patterns
 of use.

√ HELPFUL HINTS

- Holidays such as Thanksgiving and Christmas are marked on the calendar to help you better recall your
 use. Also, think about whether you used drugs on personal holidays and events such as birthdays,
 vacations, or parties.
- If you have regular drug use patterns you can use these to help you recall your use. For example, you
 may have weekend/weekday changes in your drug use or your drug use may be different depending
 where you are or whom you are with.

✓ COMPLETING THE CALENDAR

- A blank calendar is attached. Each day should contain a "0" for no drug use or a "√" for drug use.
 The time period we are talking about on the calendar is
- from ________to ______
- . In estimating your drug use, be as accurate as possible.
- DOUBLE CHECK THAT ALL DAYS ARE FILLED IN BEFORE RETURNING THE CALENDAR.
- Before you start look at the SAMPLE CALENDAR on the next page.

✓ SAMPLE CALENDAR

2000	SUN	MON	TUES	WED	THURS	FRI	SAT
							2
						0	0
S	3	4 Labor Day	5	6	7	8	9
	0	0	✓	✓	✓	0	✓
Е	10	11	12	13	14	15	16
	✓	✓	0	✓	√	0	✓
Р	17	18	19	20	21	22	23
	✓	0	0	0	0	✓	✓
_	24	25	26	27	28	29	30
Т	0	0	✓	0	0	0	✓

Substance Use Screening Questionnaire – SUSQ

"On how many days in the past 28 days have you used alcohol or other illegal substance (list prompt)?"

youthendowmentfund.org.uk

[contact]

@YouthEndowFund

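### The TLFB28 form printed in Appendix IV asks about drugs only, so if used as printed it scores alcohol-only days as abstinent and does not measure the stated primary outcome

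*Protocol*

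**What the plan says.** The body of the protocol defines the outcome consistently. The summary table at the front gives "Percent days abstinent from alcohol and/or substance use at month 6, derived from the time line follow back 28 days". Table 1 gives "Percent days abstinent from alcohol and drugs". The Primary outcome section says "We propose assessing alcohol and/ or substance use with the Time Line Follow Back method" and then fixes the derivation: "Frequency of use is calculated as percent days abstinent from alcohol and/ or other substances in the previous 28-days". The same section says the TLFB can also yield the frequency of individual substances, quantity and heavy episodic use. The Pilot study analysis section relies on this for PRQ5, through a "comparison of data derived from the TLFB for specific substances and the SRDS". ERQ13 likewise needs the type of substance used.

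Appendix IV prints the TLFB28 text, headed as an interview. It begins "To help us evaluate your drug use, we need to get an idea of what your use was like in the past", and later says "The goal is to get a picture of how many days you were using drugs". Its coding rule is a zero on a day without drug use and a tick on a day with it. Alcohol and drinking appear nowhere in the instructions.

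The single question used for eligibility and as the baseline covariate, also in Appendix IV, reads "On how many days in the past 28 days have you used alcohol or other illegal substance (list prompt". Inclusion criterion 3 accepts alcohol or substance use on at least 4 occasions in the past 28 days, so a young person who only drinks is eligible.

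**The concern.** The printed coding rule and the outcome definition give different values for the same day whenever a participant drinks and takes no drugs. The definition calls that a day of use; the form calls it abstinent. Since this is the primary outcome, three things are at stake.

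- Abstinence would be overstated for anyone with alcohol-only days, and a move from drugs to drinking would look like improvement.
- The baseline covariate, which counts alcohol, would no longer measure the same behaviour as the outcome it adjusts.
- Alcohol days that were never recorded cannot be recovered by any analysis plan. The Efficacy study analysis section pools pilot data into the final analysis, so an error in the pilot would carry through.

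**Working it through.** **1. Does the form's word for drugs include alcohol?** The other substance-use instruments in Appendix IV argue against it. GAIN-SS and SCQ8 name alcohol or drinking alongside other drugs, and so does the single substance use question. Only the TLFB text leaves it out. A reader of this appendix cannot assume that alcohol is included.

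**2. Scoring.** Percent days abstinent = 100 × (28 − days of use) / 28. Let u be all days of use under the stated definition, and a the number of those with alcohol and no drugs. The stated outcome is 100 × (28 − u)/28. The printed form gives 100 × (28 − u + a)/28. The overstatement is 100 × a/28, about 3.6 percentage points per alcohol-only day.

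| Days of use u | Alcohol-only days a | Stated outcome | Form as printed |
|---|---|---|---|
| 4 | 4 | 24/28 = 85.7% | 28/28 = 100% |
| 8 | 4 | 20/28 = 71.4% | 24/28 = 85.7% |
| 8 | 8 | 20/28 = 71.4% | 28/28 = 100% |
| 8 | 0 | 20/28 = 71.4% | 20/28 = 71.4% |

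The last row shows the limit of the problem: a day with both alcohol and drugs is ticked and scored correctly.

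**3. Covariate against outcome.** The Primary outcome section justifies the single question by its correlation with the TLFB: 0.903 for alcohol and 0.830 for drugs. A drug-only TLFB drops the behaviour for which the higher correlation is claimed.

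**4. Substance-specific data.** The printed rule allows one mark per day, either zero or tick. It has no place for which substance was used or how much.

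**5. The plan's own sample size.** Inputs from Sample size calculations: effect size 0.27, two-sided alpha 0.05, power 80%, correlation 0.4. Per arm, n = 2 × (1.960 + 0.842)² × (1 − 0.4²) / 0.27² = 180.9, so 181 per arm and 362 in all. The plan states 364, with power about 80%. The stated figure reproduces, and correcting the form does not change it.

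**6. Illustrations only.** The protocol gives neither the share of alcohol-only users nor the mean and SD of the outcome.

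- *Weaker covariate alone.* If the correlation fell from 0.4 to 0.3, 0.2 or 0 (assumed), power at 182 per arm would be about 77%, 75% or 73%.
- *Alcohol-only users fixed at 100% in both arms.* Let f be their share (assumed), and let the rest have mean m and SD s with a true effect of 0.27. The difference becomes (1 − f) × 0.27 × s and the variance (1 − f)s² + f(1 − f)(1 − m)². With m = 0.5, s = 0.35 and the correlation kept at 0.4, f = 10%, 20% or 40% gives an effect size of 0.23, 0.20 or 0.16 and power of about 68%, 56% or 36%. With m from 0.4 to 0.7 and s from 0.30 to 0.35, the power ranges are 61–73%, 46–65% and 27–48%.

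The spread across these assumptions shows that no single loss can be claimed for this trial.

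**The case against.** The strongest reply is that the Appendix IV text is a generic template and not the trial's working form. The number of days is left blank, the sample calendar is for September 2000 and shows a US holiday, and the wording addresses someone filling in a calendar alone although the heading says interview. Data go into a purpose-built online system, and tools are to be agreed with the youth panel before use. The body text plainly intends alcohol to be covered, the interviewer is to be trained, and the team reports using the TLFB for alcohol and drugs in several adolescent trials. An interviewer could simply ask about alcohol.

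Much of this stands. It means that several stronger conclusions a reader might draw are not supported:

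- That the trial will in fact measure a different outcome. The documents show only that it would if this text were followed.
- That every drinking day counts as abstinent. Only alcohol-only days do.
- That anyone who entered on alcohol alone will score 100% at both follow-ups. That needs literal use of the form, no question about alcohol and no drug use in either window.
- That substance-specific data cannot be obtained. The form's hints refer to using a certain drug, and the body text says such data will be collected. The printed coding rule just does not provide for them.
- That power falls to a particular figure. The inputs are not in the documents, and the 36% scenario needs 40% of participants to be alcohol-only, all fixed at 100%.

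The reply does not remove the conflict. This is the only TLFB text in the protocol, nothing in it tells the interviewer to ask about alcohol, and no other section corrects it. A primary outcome should not depend on interviewers departing from the printed rule.

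**Conclusion.** The point holds as a contradiction between the printed form and the stated primary outcome. If the form is followed as written, each alcohol-only day adds about 3.6 percentage points of abstinence that the outcome definition does not allow. Eight such days turn 71% into 100%, and the outcome no longer matches its covariate or the eligibility rule. That conclusion rests on the documents' wording alone. How much it would bias the comparison or reduce power depends on how common alcohol-only use is, which is unknown. It must be corrected before the form is used, because the scoring rule is wrong as printed and unrecorded days cannot be restored afterwards.

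**What to change.** Before the TLFB28 is used, make these changes in Appendix IV and in the data-collection system.

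1. Name alcohol in the instructions and in the zero/tick rule, so that a day is abstinent only if neither alcohol nor any drug was used.
2. Use the same substance list as the prompt for the single baseline question, so that covariate and outcome cover the same behaviour.
3. Mark alcohol and each drug class separately for each day. The primary outcome needs only the first change; this one is needed so that PRQ5 and ERQ13 can be answered.

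The cost is one form and database edit and a slightly longer interview. Table 4 schedules no TLFB at baseline, and the baseline question already counts alcohol, so baseline collection need not change. The sample size stays at 364 followed up.

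Separately, Appendix III describes a 90-day TLFB where the rest of the protocol uses 28 days. That is a different discrepancy, to be reconciled in the same revision.

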Consent and baseline assessment will be conducted by staff employed by Barnardo's they will be conducted in a safe, therapeutic and convenient location for the young person, this will include facilities managed by Barnardo's, community facilities accessed as part of community partnerships, children's services, school and the young person's home. Data will be collected on-line, and randomisation will be conducted independent of Barnardo's by research staff after baseline data collection has been conducted.

Inclusion criteria

- 1. Young people aged 13-17 years inclusive who are resident in the Bristol or Newport LA.
- 2. Currently involved with the police or youth justice service or at risk of offending.

At risk of offending defined as having at least one of the following risk factors, assessed on referral.

- Previously being in the secure estate.
- Currently, or previously, persistently absent from school (defined by DfE as 10% or more).
- Have been the victim of violence.
- Currently, or have attended alternative education provision.
- Received multiple suspensions from school or has been permanently excluded.
- Have a sibling or parent who has been involved in serious violence or identified as facing exploitation harm.
- Currently, or have been, in the care system.
- Have been identified as being at risk of criminal exploitation.
- Currently or have had a social worker.
- Have previously been in contact with youth justice services.
- Have been arrested, admitted an offence and released by the police with no further action.
- 3. Evidence of alcohol or substance use on at least 4 occasions in the past 28 days, assessed using a single substance use frequency question on referral to Barnardo's.
- 4. Willing and able to provide informed consent or willing to provide assent with a parent/ carer willing to provide consent.

Exclusion criteria:

- 1. Alcohol or substance severity that requires inpatient residential treatment or immediate detoxification.
- 2. Severe mental health condition requiring immediate psychiatric assessment.

Figure 3: Flow chart of recruitment processes.

Referral partners identify young people who would be suitable for MDFT

Referral partners share information with Barnardo's through secure referral form.

Barnardo's contacts young person to assess frequency of substance use, check eligibility, and gauge interest, share information sheet and privacy notice

If willing to take part young person attends for baseline assessment

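### The primary-outcome form printed in Appendix IV (TLFB28) asks only about drugs, so applied as printed it scores a drinking-only day as abstinent, although the outcome definition, entry criterion and baseline question all count alcohol

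*Protocol*

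**What the plan says.** **Outcome definition.** The summary table at the front of the protocol gives "Percent days abstinent from alcohol and/or substance use at month 6, derived from the time line follow back 28 days". Table 1 (Trial design) gives the variable as "Percent days abstinent from alcohol and drugs". The Primary outcome section says "Frequency of use is calculated as percent days abstinent from alcohol and/ or other substances in the previous 28-days", and adds that the TLFB "can yield information on the overall frequency of alcohol and substance use, frequency of individual substances, quantity of use".

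**Who enters.** Inclusion criterion 3 is "Evidence of alcohol or substance use on at least 4 occasions in the past 28 days", so a young person who only drinks can qualify.

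**Baseline covariate.** The single question at the end of Appendix IV is "On how many days in the past 28 days have you used alcohol or other illegal substance (list prompt").

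**Month-6 form.** The TLFB28 in Appendix IV is marked as given by interview. Its stated aim is to evaluate drug use. Its rule for a non-use day is "On days when you did not use drugs, you should write a" zero, and a tick marks a day with drugs. The hints, the completion rule and the closing reminder also speak only of drugs. Each day takes one mark, with no field for substance or quantity. Alcohol and drinking are not mentioned anywhere on the form.

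**The concern.** The TLFB28 is the only source for the primary outcome (front table, Table 1, Table 4). Its printed day code does not match the quantity that the protocol says it measures. Three things follow if the form is applied as printed:

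- A participant admitted on alcohol who drinks just as much at month 6 would score 100% abstinent in either arm.
- Any effect of MDFT on drinking would be absent from the primary outcome.
- The baseline covariate (alcohol plus drugs) would no longer measure the same quantity as the outcome (drugs only). The assumed pre-post correlation of 0.4 would then not apply as stated.

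This cannot be put right at analysis. With one mark per day and no substance field, a drinking day entered as zero cannot be told apart from a truly abstinent day.

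**Working it through.** **1. Wording side by side**

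| Place in protocol | Does alcohol count? |
|---|---|
| Front table, primary outcome | Yes |
| Table 1, primary outcome | Yes |
| Primary outcome section | Yes |
| Inclusion criterion 3 | Yes |
| Baseline single question, Appendix IV | Yes |
| TLFB28 form, Appendix IV | Not named; drugs only |

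Other Appendix IV instruments (GAIN-SS, SCQ-8, ESPAD) name alcohol or drinking explicitly. The word drugs on the TLFB28 therefore cannot safely be assumed to include it.

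**2. Effect on one participant's score**

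Score = (28 − days counted as use) / 28.

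| Month-6 pattern | By definition | Form as printed |
|---|---|---|
| 4 drinking-only days, no drug days | 24/28 = 85.7% | 28/28 = 100% |
| 8 drinking-only days and 4 drug days | 16/28 = 57.1% | 24/28 = 85.7% |

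**3. The plan's own sample size**

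Inputs from Sample size calculations and Table 3: d = 0.27, two-sided alpha 0.05, power 0.80, r = 0.4, 182 per arm.

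- Number per arm = 2(1.960 + 0.842)² × (1 − 0.4²) / 0.27² = 180.9, so 181 per arm or 362 in total. The t-based version gives 364, as stated.
- Power at 182 per arm = Φ(0.27 × √(182/2) / √0.84 − 1.96) = Φ(0.85) = 80.2%.

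**4. Illustration of lost power**

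The protocol gives no share q of alcohol-only users; 10–30% is assumed here. Both models assume that the form is applied literally, that the true effect is 0.27 in all users, and that r stays at 0.4.

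*Model A.* Alcohol-only users add no contrast and the SD is unchanged: d′ = (1 − q) × 0.27.

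*Model B.* Alcohol-only users all score 1.0. The others have mean m = 0.5 and SD s = 0.35 (assumed): d′ = (1 − q) × 0.27 × s / √[(1 − q)s² + q(1 − q)(1 − m)²]. For q = 0.1 this is 0.08505 / √0.13275 = 0.233.

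Power = Φ(d′ × √91 / √0.84 − 1.96).

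| q | d′, A | Power, A | d′, B | Power, B |
|---|---|---|---|---|
| 10% | 0.243 | 71.5% | 0.233 | 68% |
| 20% | 0.216 | 61.3% | 0.204 | 56% |
| 30% | 0.189 | 50.3% | 0.178 | 46% |

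If m (0.4–0.6) and s (0.3–0.4) vary together in model B, power is about 62–72% at q = 10% and 35–54% at q = 30%. Drinking-only days among people who use both alcohol and drugs are not modelled.

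**The case against.** The strongest reply is that the printed page is a stock template and not the working instrument. It has a blank for the number of days, a sample calendar headed 2000, and American holidays. Follow-up data go into a bespoke online system, and a trained researcher conducts the interview. The pilot analysis expects substance-specific TLFB data, which a single daily mark cannot supply, so a fuller interview seems to be intended. The body text names alcohol in every definition, and the team reports using the TLFB for alcohol in several adolescent trials.

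This stands as far as field practice goes: the protocol does not show that drinking days will be missed. It does not remove the contradiction. No section tells the interviewer to ask about alcohol or to depart from the printed code, and this page is the only version of the instrument that the protocol fixes.

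Three stronger readings are tempting, and the document does not support them:

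- *The primary outcome will be wrong and the primary question unanswered.* That follows only if interviewers apply the form literally, which is not established.
- *The and/or wording itself makes a drinking-only day abstinent.* The Primary outcome section rejects the GAIN because it gives individual substances and not overall use, and it describes the TLFB as giving overall frequency. Both point to any use on a day, so this reading is strained.
- *The trial has 46–68% power.* Those figures rest on an assumed alcohol-only share, an assumed mean and SD, an equal effect in drinkers and drug users, and an unchanged r. They are not estimates for this trial.

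**Conclusion.** The concern holds as a contradiction in the primary-outcome instrument. The TLFB28 as printed does not ask about alcohol, while the outcome definition, the entry criterion and the baseline covariate all count it.

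Confidence in the wording mismatch is high. The size of the consequence is conditional. For a participant with four drinking-only days, the error is 14.3 percentage points (100% against 85.7%) if the form is followed literally. For the trial, the direction is a loss of power, but its amount cannot be derived from the protocol. The illustrative 68–72%, 56–61% and 46–50% at alcohol-only shares of 10%, 20% and 30% depend on the model and on inputs that are not in the document.

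It should be corrected before month-6 data are collected, because the loss could not be recovered afterwards.

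**What to change.** Before the first month-6 interview:

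- Reword the TLFB28 aim, day codes, hints and completion rule so that a day is marked as used if any alcohol or any listed drug was taken, and as abstinent only if neither was.
- Use the same substance prompt list as the baseline single question.
- State the same rule in one scoring sentence in the Primary outcome section.
- As a minor editorial step, replace and/or in the outcome definition with wording that means neither alcohol nor any listed drug.

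Timing matters because pilot participants are pooled into the final analysis. A correction made after pilot follow-up has begun would leave early participants measured differently.

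The cost is a few sentences on the form and one in the protocol. The follow-up target of 364 does not change, and no participants or extra interview are needed.
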